4.3 Handling of repeated and unscheduled measurements

All repeated and unscheduled measurements will be presented in the data listings, where applicable. Repeated measurements are defined as more than 1 measurement at the same timepoint. For example, the same laboratory parameters assessed twice using the same batch of blood samples due to issues with the first assessment. The following general rules will apply to all repeated and unscheduled measurements:

- Unscheduled and repeated measurements prior to the first dose of study treatment will be used in the determination of Baseline and hence in the calculation of summary statistics at Baseline;
- Unscheduled and repeated measurements performed after the first dose of study treatment will not be included in the calculation of change from Baseline, summary measures such as minimum, maximum, average and last post-Baseline value calculated for the summaries of laboratory data (see Section 8.3), vital signs (see Section 8.4.1) and 12-lead ECG (see Section 8.4.2), or summary statistics, i.e. only the scheduled measurements will be used and summarized. Similarly, only scheduled visits will be used in the summaries of shifts from Baseline to the worst post-Baseline CTCAE severity grade for laboratory data (see [Section 8.3](#)).
- For the summaries of the investigator's overall tumor response assessment, protocol-defined windows will be applied to all post-Baseline tumor assessments (scheduled or

unscheduled, but excluding tumor assessments performed at the SFU visit), as detailed in Section 10.1.2. Those tumor assessments which fall outside of the window will be considered as unscheduled assessments and not included in the summaries.

- Best overall response, DOR and PFS derivations will use data from all scheduled and unscheduled tumor assessments.
- All data from unscheduled visits will, however, be included on the relevant data listings.

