10.1.1 Definitions of the antitumor activity endpoints

The following endpoints are defined based on RECIST (Version 1.1) which standardizes solid tumor measurements and provides guidelines for the objective assessment of changes in tumor size during anti-cancer treatment.

Appendix 9 (Section 11.9) of the protocol contains the RECIST 1.1 guidelines to be used in this study, adapted from Eisenhauer (2009), and includes the definitions of target and non-target lesions, the definitions of target and non-target lesion responses at each tumor assessment, the criteria for determining overall tumor response at each tumor assessment based on target lesion response, non-target lesion response and the presence/absence of new lesions, and a participant's best overall response (BOR).

At each post-Baseline tumor assessment, the investigator will record responses for target lesions and non-target lesions, whether or not there has been an appearance of any new lesions, and the participant's overall tumor response based on their target lesion response, non-target lesion response and the presence/absence of new lesions. Note that target lesion response and non-target lesion response assessments will be based on the changes in the pre-existing lesions at Baseline and the appearance of new lesions will only factor in the determination of an overall tumor response of PD at that tumor assessment visit (i.e. per Tables A and B in Section 11.9.2 of Appendix 9 of the protocol).

Objective response rate (ORR) is defined as the percentage of participants with a BOR of complete response (CR) or partial response (PR) during Part A.

Disease Control Rate (DCR) is defined as the percentage of participants with a BOR of CR, PR, or stable disease (SD) during Part A.

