Best overall response (BOR) is defined for each study participant as the best overall tumor response from each tumor assessment (scheduled and unscheduled assessments performed between Days 21 and 28 of every even cycle of study treatment) according to the RECIST criteria for changes in target and non-target lesions and the appearance of new lesions. Best overall response is determined from the start of study treatment until documented objective disease progression or the date of subsequent anti-cancer therapy (systemic therapy, surgery or radiotherapy for cancer), whichever occurs first. If anti-cancer therapy is started on the same day as a tumor assessment, then the overall response from that assessment will be used in the derivation of BOR. For a BOR of SD, a participant's tumor measurements must have met the SD criteria at least once after the start of study treatment at a minimum interval of no less than 6–8 weeks (42–56 days).

For Part A of this study, BOR determination requires confirmation of CR or PR responses at a subsequent assessment ≥ 4 weeks (28 days) after the criteria for CR or PR responses are first met. In addition, Table C in Appendix 10.9 of the protocol provides the derivation of BOR when confirmation of CR and PR responses are required. Confirmed BOR and unconfirmed BOR will be derived programmatically based on the overall tumor assessment data recorded on the eCRF

by the investigator and using the detailed guidance included in the Derivation of Efficacy Endpoints document Version 0.6 (dated 21 January 2022).

Duration of response (DOR) will be calculated for participants with a confirmed BOR of CR or PR as the time in days from the start date of the confirmed CR or PR to the first date that recurrent or progressive disease is objectively documented (i.e. according to the RECIST guidelines). This will be referred to as the duration of confirmed response and the following calculation will be performed:

$$\begin{aligned} & \text{Duration of Confirmed Response} \\ & = (\text{Date of First Objective Disease Progression} \\ & \quad - \text{Start Date of Confirmed CR or PR Response}) + 1 \end{aligned}$$

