Bar charts will also be produced for overall tumor response rate by treatment group for each visit. In addition, waterfall plots of participants' percentage change from Baseline in the sum of dimensions for all target lesions will be presented by treatment group and visit. The individual participants' bars will be colored by overall tumor response at the visit.

Confirmed BOR and unconfirmed BOR for each participant will be derived programmatically using the investigator's overall tumor response assessments (scheduled and unscheduled) performed between Days 21 and 28 of Cycle 2 and each subsequent even cycle of study treatment and the RECIST criteria. Whether a BOR of CR or PR is confirmed or unconfirmed will be indicated on this listing. Using a participant's confirmed BOR and unconfirmed BOR, whether the participant achieves an objective tumor response (i.e. a BOR of CR or PR) and/or disease control (i.e. a BOR of CR, PR or SD) during study treatment will be determined based on both confirmed BOR and unconfirmed BOR. These derived data will be listed for the SS.

Confirmed BOR and unconfirmed BOR will be summarized using frequency counts and percentages. Bar charts will also be produced for confirmed BOR and unconfirmed BOR by treatment group.

The number and percentage of participants achieving objective tumor response and disease control (ORR and DCR) based on confirmed BOR and unconfirmed BOR will be presented and, if data allow, exact 95% confidence intervals for binomial proportions will be calculated using the Clopper-Pearson method and presented for the response rates. In the calculation of ORR and DCR, the denominator will include all participants in the analysis set. Objective response rate and DCR (based on confirmed BOR and unconfirmed BOR) will also be summarized in bar charts by treatment group overall and by tumor type and ECOG performance status at Baseline.

In addition, waterfall plots of each participant's best percentage change from Baseline in the sum of the dimensions for all target lesions will be presented by treatment group overall and by tumor type and ECOG performance status at Baseline with the individual participants' bars colored by confirmed BOR and unconfirmed BOR.

The summaries and analyses of DOR, PFS and OS will be carried out as described below, if the data allow.

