Best overall response (BOR) is defined for each study participant as the best overall tumor response from each tumor assessment (scheduled and unscheduled assessments performed every 8 weeks from Day 1 of Cycle 1 (± 7 days)) according to the RECIST criteria for changes in target and non-target lesions and the appearance of new lesions. Best overall response is determined from the start of study treatment (first dose of UCB6114) until documented objective disease progression or the date of subsequent anti-cancer therapy (systemic therapy, surgery or radiotherapy for cancer), whichever occurs first. If anti-cancer therapy is started on the same day as a tumor assessment, then the overall tumor response from that assessment will be used in the derivation of BOR. If a participant does not have objective disease progression and does not start a subsequent anti-cancer therapy, then all tumor assessments (scheduled and unscheduled) up to the SFU visit will be included in the derivation of BOR. For a BOR of SD, a participant's tumor measurements must have met the SD criteria at least once after the start of study treatment at a minimum interval of no less than 49 days.

For Part A1, BOR determination requires confirmation of CR or PR responses at a subsequent assessment ≥ 4 weeks (28 days) after the criteria for CR or PR responses are first met, however, an unconfirmed BOR will also be derived for each participant for the purpose of reporting (as

described below in [Section 10.1.2](#)). Table C in Appendix 11.9 of the protocol and Table 1 and subsequent text in the Derivation of Efficacy Endpoints document provides detail on the derivation of BOR when confirmation of CR and PR responses is required. The definition of an unconfirmed BOR is also included in this document. Although the derivation of unconfirmed BOR does not include the requirement for a CR or PR response to be confirmed ≥ 4 weeks (28 days) after the initial response, a participant's CR or PR response may, in fact, be confirmed at a subsequent assessment ≥ 4 weeks (28 days) after the criteria for the CR or PR response are first met.

Confirmed BOR and unconfirmed BOR will be derived programmatically based on the overall tumor assessment data recorded on the eCRF by the investigator.

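### Part A best overall response is defined on two different sets of scans, and its stable disease minimum is a range of 42 to 56 days instead of one cut-off

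*SAP*

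**What the plan says.** **Which scans count.** Part A SAP Section 4.3 applies a visit window to the summary of the investigator's overall tumor response. It then states separately: "Best overall response, DOR and PFS derivations will use data from all scheduled and unscheduled tumor assessments". Section 10.1.1 defines BOR from "scheduled and unscheduled assessments performed between Days 21 and 28 of every even cycle of study treatment". Section 10.1.2 says confirmed and unconfirmed BOR will be programmed from scheduled and unscheduled assessments "performed between Days 21 and 28 of Cycle 2 and each subsequent even cycle of study treatment".

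**Confirmation.** Section 10.1.1: "BOR determination requires confirmation of CR or PR responses at a subsequent assessment ≥ 4 weeks (28 days) after the criteria" are first met.

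**Stable disease.** Section 10.1.1 requires the SD criteria to be met at least once after treatment start, "at a minimum interval of no less than 6–8 weeks (42–56 days". DCR is the "percentage of participants with a BOR of CR, PR, or stable disease (SD) during Part A", so this rule feeds straight into DCR.

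**Comparison.** The Part A1 SAP, Section 10.1.1, gives one value for the same rule, "at a minimum interval of no less than 49 days". It also says that, without progression or new anti-cancer therapy, all scans up to the safety follow-up visit enter BOR.

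**The concern.** Two programmers could each follow the Part A SAP and derive different BORs. One would take every scan, as in Section 4.3. The other would filter to Days 21-28 of even cycles, as in Sections 10.1.1 and 10.1.2. The filter names unscheduled scans explicitly, so it can be read as an inclusion rule and not only as a description of the schedule. It is also narrower than the window used for the by-visit table in the same section.

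The SD minimum cannot be programmed as written, because a range has no single pass/fail point. The range also straddles the first scheduled scan, so the choice within it decides the classification.

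At stake is whether confirmed objective response rate (ORR), DCR and the set of participants entering duration of confirmed response can be reproduced from the SAP. All of these are exploratory in Part A.

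**Working it through.** **Inputs (Part A SAP).** Cycles of 28 days (Section 3.2.2). BOR window of Days 21-28 of even cycles (10.1.1, 10.1.2). By-visit window of Days 21-28 ±2 days, that is Days 19-30 (10.1.2). Confirmation at 28 days or more and SD minimum of 42-56 days (10.1.1). Part A1 SD minimum of 49 days (Part A1 SAP 10.1.1).

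**1. Reproduce the plan's own window.** Study day = 28 × (cycle − 1) + cycle day. Cycle 2 Day 19 = 28 + 19 = 47 and Cycle 2 Day 30 = 28 + 30 = 58. This matches the Day 47 to 58 window stated in Section 10.1.2.

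**2. BOR window in study days.** Cycle 2: 28 + 21 = 49 to 28 + 28 = 56. Cycle 4: 84 + 21 = 105 to 84 + 28 = 112.

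**3. Confirmation scans under the literal window.**
- A scan exactly 28 days after a Cycle 2 response falls on study Days 49 + 28 = 77 to 56 + 28 = 84, which is Cycle 3 Days 21-28. That is an odd cycle, so it is outside the window for all 8 possible first-response days.
- The earliest retained confirmation comes 105 − 56 = 49 to 105 − 49 = 56 days after first response (105 − 50 = 55 for a Day 22 scan). Every scan 28 to 48 days after the response is dropped.
- Widening to Days 19-30 moves the start of the Cycle 4 window to Day 103. The earliest gap is then 103 − 58 = 45 to 103 − 47 = 56 days.
- The gap from a Cycle 2 scan to a Cycle 4 scan in the Day 21-28 window is 49 to 112 − 49 = 63 days. That always satisfies the 28-day rule.

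**4. By-visit table against BOR.** The table accepts 12 cycle days (19-30) and the BOR text accepts 8 (21-28). Scans on Days 19, 20, 29 and 30 count in one and not in the other.

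**5. SD minimum against the first scan.** Elapsed days = study day − 1; inclusive days = study day. Number of window days on which a first scan can support SD:

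| Minimum | Days 49-56, elapsed | Days 49-56, inclusive | Days 47-58, elapsed | Days 47-58, inclusive |
|---|---|---|---|---|
| 42 days | 8 of 8 | 8 of 8 | 12 of 12 | 12 of 12 |
| 49 days | 7 of 8 | 8 of 8 | 9 of 12 | 10 of 12 |
| 56 days | 0 of 8 | 1 of 8 | 2 of 12 | 3 of 12 |

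The target scan, Cycle 2 Day 22, is study Day 50, or 49 days elapsed. It passes at 42 and at 49 and fails at 56 under either counting convention.

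**6. Size in one cohort.** Section 10.1.2 takes all participants in the analysis set as denominator. With an assumed 6 participants, each one whose SD rests on the first scan alone moves DCR by 1/6 = 16.7 points.

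**The case against.** The best case for the plan is that the Day 21-28 phrase only describes the scan schedule. Section 4.3 is where the SAP decides which scans count, and it windows only the by-visit summary. Section 10.1.2 uses exclusion wording for that summary alone. The Part A1 SAP has a parallel phrase about scans every 8 weeks and then includes all scans up to safety follow-up, so there the phrase is plainly descriptive. This may well be the intent. Part A, however, lacks the Part A1 sentence that settles it, and it states the limit twice.

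A reader might infer that the confirmation rule is defeated. It is not: 28 days is a minimum, and the Cycle 4 scan meets it. For the two readings to differ on a confirmed response, a responder needs an off-schedule confirmatory scan and then no usable confirmation at Cycle 4, for example partial response at Cycle 2 and Cycle 3 Day 22 followed by progression. The documents give no frequency for this. Unconfirmed BOR, with ORR and DCR based on it, is reported alongside.

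A reader might also infer that DCR as a whole could swing from 100% to about 0%. The documents do not support that. The choice matters only for participants whose SD rests on the first scan alone. Even at 56 days, study Days 57-58 still qualify within the ±2 day window. A floor of 42 days is arguably the natural reading of the range.

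Finally, the Derivation of Efficacy Endpoints document, version 0.6, and the protocol's Table C are cited for BOR and are not at hand; they may resolve both points. That does not cure contradictory SAP text. Section 1 says the SAP supplies all that is needed for the Part A analysis, and the Part A1 SAP cites the same version 0.6 yet still states its own single SD value.

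**Conclusion.** The text is wrong as written on two counts. Sections 10.1.1 and 10.1.2 contradict Section 4.3 on the scans that enter BOR, and the SD minimum is a range where a threshold is needed.

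Taken literally, the first drops confirmatory scans 28 to 48 days after a Cycle 2 response and scans on Days 19-20 and 29-30. The second leaves DCR open for participants whose only support for SD is the first scan, at 16.7 points each in an assumed cohort of 6. The study-day figures assume cycles start on schedule.

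The documents do not show that any participant is affected, or that the narrow reading is the intended one. The endpoints are exploratory and descriptive, and the primary safety and dose-limiting toxicity endpoints are untouched. The defect is one of reproducibility and should be corrected before the final Part A analysis.

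**What to change.** - In Sections 10.1.1 and 10.1.2, delete the Day 21-28 even-cycle qualifier from the BOR text. State that BOR uses all scheduled and unscheduled assessments from first dose until objective progression or new anti-cancer therapy, consistent with Section 4.3. Retain the existing rule for therapy that starts on the day of a scan.
- Keep visit windows for the by-visit summary of overall response only.
- Replace the SD range with one number of days from first dose, and say whether Day 1 is counted. It should be no later than the lower edge of the first-scan window including the ±2 days: study Day 47, or 47 − 1 = 46 days elapsed. For example, 42 days would do.
- Explain any difference from the 49 days in Part A1. That value equals the lower edge of Part A1's own first window (Day 57 − 7 = Day 50, 49 days elapsed). In Part A it would reject 3 of the 12 window days on elapsed counting.
- Align the Derivation of Efficacy Endpoints document with these choices.

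The cost is SAP wording, a matching edit to the derivation document and a check of the BOR program. No new scans or data are needed.

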Duration of response will also be calculated for participants with an unconfirmed BOR of CR or PR (which may either be confirmed at a later tumor assessment or unconfirmed) as the time in days from the start date of the CR or PR to the date of the first documented objective disease progression (i.e. according to the RECIST guidelines). The following calculation will be performed:

$$\begin{aligned} & \text{Duration of Unconfirmed Response} \\ & = (\text{Date of First Objective Disease Progression} \\ & \quad - \text{Start Date of CR or PR Response}) + 1 \end{aligned}$$

For the purpose of a sensitivity analysis of both duration of confirmed response and duration of unconfirmed response, the above calculations will take into consideration the occurrence of both objective disease progression (per RECIST 1.1) and clinical disease progression (as described in Appendix 11.9 of the protocol and as determined by the investigator and recorded as a reason for study treatment discontinuation on the eCRF), whichever occurs first. If clinical disease progression occurs on the same date that a participant's objective disease progression is determined, then the participant will be included in the sensitivity analyses as having objective disease progression.

The following calculations will therefore be performed for the sensitivity analyses:

$$\begin{aligned} & \text{Duration of Confirmed Response} \\ & = (\text{Date of First Objective or Clinical Disease Progression} \\ & \quad - \text{Start Date of Confirmed CR or PR Response}) + 1 \end{aligned}$$

$$\begin{aligned} & \text{Duration of Unconfirmed Response} \\ & = (\text{Date of First Objective or Clinical Disease Progression} \\ & \quad - \text{Start Date of CR or PR Response}) + 1 \end{aligned}$$

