For participants who die without objective disease progression, duration of confirmed response and duration of unconfirmed response will be censored on the date of death, regardless of cause. For a participant who discontinues early from Part A of the study with no objective disease progression, duration of confirmed response and duration of unconfirmed response will be censored on the date of their last available (scheduled or unscheduled) tumor assessment at which a lack of objective disease progression was determined. Participants who discontinue study treatment but who do not have documented objective disease progression (i.e. according to the RECIST guidelines), duration of confirmed response and duration of unconfirmed response will be censored at the date of their last available (scheduled or unscheduled) tumor assessment

at which a lack of objective disease progression was determined. Such participants might include those that are ongoing in Part A at the time of any defined data cut-off.

In the sensitivity analyses of duration of confirmed response and duration of unconfirmed response, the same censoring rules will apply except that the date of last contact will be used for the censoring of participants who discontinue early from Part A, complete Part A of the study or are ongoing in the study at a data cut-off for Part A without objective disease progression, clinical disease progression or death.

Date of last contact will be the latest of the dates of premature study termination and of last contact recorded on Study Termination eCRF page, the date of death, the date of last dose of study treatment, the dates of all visits, AE start and end dates (with partial dates imputed as earliest possible) and the date of contact recorded on the Survival Safety Follow-up and Survival Final Follow-up eCRF forms.

Further details on the derivation of duration of confirmed response and duration of unconfirmed response are included in the Derivation of Efficacy Endpoints document Version 0.6 (dated 21 January 2022).

Progression-free survival (PFS) will be calculated as the time in days from the first dose of study treatment to the date of the first documented objective disease progression (i.e. according to the RECIST guidelines), or death due to any cause, whichever occurs first. The following calculation will be performed:

$$PFS = (Date\ of\ Objective\ Progressive\ Disease/Death - Date\ of\ First\ Dose) + 1$$

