Participants who die due to any cause without a documented objective disease progression will be considered to have progressed on the date of their death. Participants who do not have any post-Baseline tumor assessments will be censored on the date of their first dose of study treatment. Participants who discontinue early from Part A or discontinue study treatment without documented objective disease progression or death, will be censored on the date of their last available (scheduled or unscheduled) tumor assessment at which a lack of objective disease progression was determined. Participants who start anti-cancer therapy during Part A without a prior documented objective disease progression will be censored on the date of their last available (scheduled or unscheduled) tumor assessment prior to the initiation of the subsequent anti-cancer therapy. If anti-cancer therapy starts on the same date as the participant's tumor assessment and determination of objective disease progression, or the participant's death (due to any cause), then the participant will not be censored and the participant will be included as having an uncensored event on this date. This censoring rule will also be applied to participants who are ongoing at any data cut-off for an analysis of Part A data who have no documented objective disease progression. The use of anti-cancer therapy during Part A will be identified via ongoing medical review of the concomitant medications together with the start dates of further anti-cancer therapy information recorded on the survival follow-up pages of the eCRF.

As a sensitivity analysis, PFS will also be calculated as the time in days from the first dose of study treatment to the date of the first documented objective disease progression (per RECIST 1.1), the date of clinical disease progression, as determined by the investigator, or the date of death due to any cause, whichever occurs first. Last contact date (as defined above for DOR) will be used for the censoring of participants still alive with no reported disease progression

(objective or clinical). The same rules described above for the censoring of participants who start anti-cancer therapy will be applied in this sensitivity analysis.

Further details on the derivation of PFS are included in the Derivation of Efficacy Endpoints document Version 0.6 (dated 21 January 2022).

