Overall survival (OS) will be calculated as the time in days from the date of first dose of study treatment to the date of death from any cause. Participants will be followed up to ascertain their survival status at the SFU visit (within 30 days after their last dose of study treatment) and at the Final Visit (3 months after their last dose of study treatment); they will not be followed up beyond this timepoint.

The following calculation will be performed:

$$OS = (Date\ of\ Death - Date\ of\ First\ Dose\ of\ Study\ Treatment) + 1$$

For participants who discontinue early from Part A of the study or who discontinue study treatment due to disease progression but continue in the study, who complete the Part A, or who are ongoing in the study at a data cut-off for Part A, but are not known to have died, OS will be censored on the date of their last contact.

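### Every planned DOR analysis censors deaths that PFS counts as events; the sensitivity DOR and PFS also run to last contact, past the scheduled scans

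*SAP*

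**What the plan says.** The Part A and Part A1 SAPs handle death in the same way in Section 10.1.1.

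- **DOR.** The only event is objectively documented progression. For a responder who dies without it, "duration of confirmed response and duration of unconfirmed response will be censored on the date of death, regardless of cause". Living participants without progression who discontinue are censored at their last tumor assessment.
- **PFS.** "Participants who die due to any cause without a documented objective disease progression will be considered to have progressed on the date of their death".
- **Sensitivity DOR.** Clinical progression is added as an event, but "the same censoring rules will apply except that the date of last contact will be used for the censoring of participants who discontinue early". Death therefore stays censored. In Part A, last contact also applies to completers and to participants ongoing at a cut-off. In Part A1 it applies only to early discontinuers.
- **Sensitivity PFS, both parts.** The events are objective progression, clinical progression and death. "Last contact date (as defined above for DOR) will be used for the censoring of participants still alive with no reported disease progression" of either kind. Participants who start new anti-cancer therapy keep the main rule.

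Clinical progression is the investigator's determination, "recorded as a reason for study treatment discontinuation on the eCRF". Date of last contact is the latest of several dates, including "the date of contact recorded on the Survival Safety Follow-up and Survival Final Follow-up eCRF forms". The Final Visit is 3 months after last dose. Section 10.1.2 summarizes DOR and PFS by Kaplan-Meier percentiles and by rates at 3, 6 and 9 months.

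**The concern.** A responder who dies progression-free has a PFS event and a censored response on the same day, and neither SAP gives a reason. Kaplan-Meier takes a censored person to face the same future as those still at risk. A dead responder has no remaining response, so the estimate is raised by exactly the outcome it should reflect. Because the sensitivity DOR repeats the rule, nothing in the planned output would show the effect.

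The last-contact rule raises a lesser problem. Scheduled scans end at the SFU visit, and the SAP's source for clinical progression closes when treatment stops. Visits, AE dates and survival contacts after that say little about progression, yet the time up to them is counted as progression-free.

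What is at stake is the reading of small exploratory summaries: cohorts of 3 to 6 evaluable participants in Part A and up to 8 in Part A1. At that size, one death or one long unassessed tail visibly moves a median or a 3-month rate.

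**Working it through.** The SAPs state no DOR or PFS assumption, event count or power, so there is no figure to reproduce. The rules come from Section 10.1.1. All times and hazards below are assumed.

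**1. Direction for DOR.** At a death with n at risk, the Kaplan-Meier factor is 1 − 1/n if death is an event and 1 if it is censored. The person leaves the risk set at that time either way, so all other factors are equal. Censoring the death can only raise S(t) or leave it unchanged.

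**2. Three responders** (days from start of response: death 60, progression 112, progression 168), with 3 months taken as Day 91.
- As written: no event by Day 91, so S(91) = 1.00.
- Death as an event: S(91) = 1 − 1/3 = 0.67.

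**3. Six responders** (progression at 57, 113, 169 and 225; death at 85 and 140).
- Deaths censored: S = 5/6 = 0.833 at 57; × 3/4 = 0.625 at 113; × 1/2 = 0.312 at 169. Median 169 days.
- Deaths as events: S = 0.833, 0.667, 0.500 at 57, 85, 113. Median 113 days, taking the first time S reaches 0.5. Averaging over the flat stretch would give (113 + 140)/2 = 126.5.

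**4. Constant hazards.** With progression hazard a and death hazard b, the median is ln2/a with deaths censored and ln2/(a + b) with deaths as events. The ratio is (a + b)/a = 1/(1 − p), where p = b/(a + b) is the share of first events that are deaths.

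| p | 5% | 10% | 20% | 30% | 40% |
|---|---|---|---|---|---|
| Ratio of medians | 1.05 | 1.11 | 1.25 | 1.43 | 1.67 |

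**5. Last-contact censoring** (3 months taken as 91 days; no progression, death or new therapy; Final Visit attended).
- Dosed on Days 1 and 15, no post-Baseline scan: main PFS is censored on Day 1, sensitivity PFS at 15 + 91 = Day 106. The participant counts as progression-free at 3 months without a scan.
- Stops after Cycle 2: last dose Day 43, scan Day 50, SFU Day 43 + 30 = 73, Final Visit Day 43 + 91 = 134. The stretch after the last scan is 134 − 73 = 61 days with an SFU scan and 134 − 50 = 84 days without one.

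With the events held fixed, a later censoring date enlarges later risk sets, so S(t) can only rise or stay the same.

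**6. Simulated PFS**, 20,000 participants per scenario. Assumptions: scans on Day 50 and every 56 days; an SFU scan 30 days after a stop not due to progression; last contact 91 days after the stop; death hazard 1/400 per day; no new therapy. Cells are 3-month / 6-month rates.

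| Progression median; share with clinical progression; stop hazard per day | True | Main | Sensitivity, last contact | Sensitivity, last scan |
|---|---|---|---|---|
| 60 d; 0%; 1/150 | 0.282 / 0.075 | 0.391 / 0.071 | 0.437 / 0.136 | 0.391 / 0.071 |
| 60 d; 30%; 1/150 | 0.280 / 0.076 | 0.421 / 0.088 | 0.410 / 0.136 | 0.363 / 0.069 |
| 120 d; 0%; 1/150 | 0.474 / 0.221 | 0.548 / 0.191 | 0.590 / 0.287 | 0.548 / 0.191 |
| 120 d; 30%; 1/150 | 0.469 / 0.221 | 0.567 / 0.223 | 0.567 / 0.291 | 0.524 / 0.194 |
| 120 d; 15%; 1/300 | 0.475 / 0.224 | 0.587 / 0.239 | 0.580 / 0.271 | 0.560 / 0.221 |

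With the same events, last contact gives the higher rate in every row, and last-scan censoring is nearer the true value at both times. It is not exact: in the third row its 6-month rate of 0.191 lies below the true 0.221.

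**The case against.** The strongest reply on DOR is that the SAP defines it as time to objectively documented progression, so censoring death follows the definition. Section 3.9 of neither SAP lists a DOR departure from the protocol, and the protocol appendix and the Derivation of Efficacy Endpoints document were not available here. It stands that counting death changes the event definition and should be declared as such. It does not remove the problem: the result is presented as duration of response beside a PFS that counts the same deaths, and no version with death counted is planned.

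On last contact, more of the reply stands. A reader might infer that progression cannot be recorded after treatment stops. The documents do not support that: Section 4.3 (Part A) and Section 4.5 (Part A1) admit unscheduled assessments to DOR and PFS, and the survival follow-up listing in Section 10.1.2 includes disease assessments since the end of treatment. Ascertainment there is thin, not absent. SFU scans shorten the unassessed stretch, and the new-therapy rule limits who is affected in PFS. Last contact is also a proper censoring date for the death component of the sensitivity PFS.

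A reader might further infer that the sensitivity analysis is intended as the stricter one, or that it must exceed the main result. Neither SAP states such an intent, and the added clinical-progression events pull the other way. In the second simulated row the sensitivity PFS median is 64 days against 70 for the main analysis.

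**Conclusion.** The DOR point holds in both SAPs. Its direction is certain whenever a responder dies progression-free. Its size depends on how often that happens: nil if it never does, and a median 11% to 43% longer if deaths are 10% to 30% of first events under constant hazards.

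The last-contact point holds as a secondary one, for progression only and with the events held fixed. It covers sensitivity PFS in both parts, sensitivity DOR broadly in Part A, and sensitivity DOR in Part A1 for early discontinuers only. For participants still on treatment at a cut-off, the excess is at most about one scan interval.

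It would go too far to conclude that all the planned durations are inflated by these rules. Main PFS uses neither. The endpoints are exploratory, descriptive and analyzed if the data allow, and the SAPs attach no decision rule to them. The change is worth making because it is cheap and brings DOR into line with the plan's own PFS rule.

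**What to change.** In Section 10.1.1 of both SAPs:

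- Count death from any cause as a DOR event, for confirmed and unconfirmed response and in the sensitivity DOR. The death-censored version may be kept as a labelled sensitivity analysis.
- In the sensitivity DOR and PFS, keep clinical progression as an event but censor event-free participants at the last tumor assessment, as in the main analysis. Reserve last contact for OS. The data cut-off date is not a suitable substitute, because it is never earlier than the last contact known at that cut-off.

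The cost is SAP wording, censoring flags and alignment of the Derivation of Efficacy Endpoints document. If the protocol defines DOR without death, an entry in Section 3.9 is also needed. No new data are required. Durations and rates may come out somewhat shorter. If Part A or Part A1 is already locked, Section 1 of the SAPs allows the revised analysis to be added and explained in the CSR.
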